hyperglycemia has a deleterious vascular effect. However, these indices do not directly measure macrovascular flow or microvascular perfusion, vital issues for the tissues per se. A very few human studies have assessed hyperglycemia's effects on microvascular perfusion. In the eye acute hyperglycemia increased retinal flow (measured by videomicroscopy) (12, 13). By contrast, in skin hyperglycemia decreased flow (measured by laser-Doppler flowmetry) (Cuypers, 2000 #6750). Brain perfusion has been measured by arterial spin-labeling MRI in rats (but not in humans) and declined with overnight hyperglycemia with suppressed insulin (27). None of these studies addressed the interaction between insulin or insulin resistance and perfusion and none involved skeletal or heart muscle. CEU provides a noninvasive method to measure two components of microvascular perfusion i.e. microvascular blood volume (MBV) and microvascular flow velocity (MFV). The product of these variables is a measure of microvascular perfusion (28). Our laboratory has extensive experience using CEU to measure perfusion in human cardiac and skeletal muscle. We have previously reported that insulin, exercise, GLP-1, mixed meal ingestion, and angiotensin II each enhance skeletal muscle microvascular perfusion by recruiting under perfused capillaries and increasing MBV (15, 16, and 29). We have also shown that insulin's effect to recruit skeletal muscle microvasculature is lost in insulin resistant subjects with metabolic syndrome, obesity, or when otherwise healthy subjects are rendered insulin resistant by lipid infusion. We have also shown that in healthy volunteers insulin and GLP-1 can each increase MBV in human myocardium. Raising plasma free fatty acid concentrations blunts the effect of insulin on the myocardium as well as on skeletal muscle (25, 29). In these studies of either skeletal or cardiac muscle, MFV was not significantly changed. In a similar vein, an early study using CEU reported that meal ingestion in individuals with type 2 diabetes decreased MBV without affecting MFV (30). As noted earlier, meal ingestion is a more complex stimulus than hyperglycemia per se. A recent CEU study used the pancreatic clamp to provoke hypoinsulinemic hyperglycemia (~220 mg/dl) and reported a decreased myocardial blood flow reserve (provoked by an adenosine agonist) in healthy volunteers (31). No measure was obtained of the direct effect of hyperglycemia. Interestingly, the inhibitory effect of hyperglycemia was attributed to changes in MFV without any significant effect on MBV. The study did not test whether the octreotide (used in the pancreatic clamp) per se affected microvascular responses. Given the scant available data regarding the effect of hyperglycemia on microvascular perfusion in either skeletal or cardiac muscle we propose to establish the vascular impact of acute hyperglycemia in the clinical setting in normal healthy controls.

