	Sponsor
	UVa Statistician. Insert name Answer/Response:
	UVa Investigational Drug Service (IDS)
	X Other: Specify Answer/Response:
	Randomization table obtained from online source-copy included

2. What are the statistical considerations for the protocol?

By design, each of the above protocols affords a paired comparison of the changes which occur between measurements obtained at baseline and at the end of the infusion protocol. Principal endpoints are the changes in microvascular perfusion in both skeletal and cardiac. Referring to Fig 1 for protocol A this comparison will indicate whether 3 ½ hours of octreotide infusion with basal insulin replacement and maintenance of euglycemia per se influences microvascular perfusion in either tissue. As noted above, if octreotide has no specific effect on the primary microvascular endpoint (MBV) then in protocols B, C, and D, we believe paired comparison of baseline and end of study variables will be justified.

This may prove advantageous as it may minimize the effect of day-to-day or week to week variations in responses resulting from uncontrolled variables (diet, exercise, emotional stress etc.) For protocol B this comparison will address whether hyperglycemia for 3 ½ hours in the setting of octreotide infusion, and basal insulin replacement affects microvascular perfusion. Combined protocols A and B analyzed using a 2-way ANOVA will allow analysis of whether time or treatment differences exist and will delineate the effect of hyperglycemia per se on skeletal and cardiac muscle microvascular perfusion, independent of any effect of octreotide per se. In protocols C and D introduce hyperinsulinemia as additional variable under either hyperglycemic or euglycemic conditions with octreotide infusion persisting throughout. Comparing the baseline measurements (C-1) to those obtained at the end of the study (C-2) addresses whether insulin affects microvascular perfusion in the setting of hyperglycemia. Comparison of the

Version Date: November 16, 2017

Page Number: 5 of 34

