changes of indices of microvascular perfusion between protocol C and D (2-way ANOVA) will provide a measure of whether acute hyperglycemia induces resistance to insulin's action to enhance cardiac and skeletal muscle microvascular perfusion. A number of other comparisons can be made from the four infusion protocols. Thus, comparing measures at D1 and A2 will allow assessment of the reproducibility of measures of microvascular function following three and half hours of octreotide with basal insulin replacement and euglycemia). For macrovascular function we will use FMD as the primary endpoint for macrovascular endothelial function and PWV as the primary endpoint for measures of central aortic stiffness. This was selected because we know from prior experiments that physiologic hyperinsulinemia in healthy subjects enhances FMD. While it is difficult to power all endpoints of the study at this point in time, we note that our published studies have examined vascular insulin action in cohorts of 12-18 subjects and we have found that 12-14 subjects are sufficient to detect a 30% difference in microvascular function in response to insulin. Thus, with 20 subjects per group, and with at least 16 subjects completing all four studies we expect to have at least an 80% power of detecting a 30% between-group mean difference in each endpoint. It will be particularly interesting if the myocardial microvasculature does not respond to insulin by enhanced microvascular perfusion during the hyperglycemic clamp (protocol C) as we have found in healthy adults (25). To our knowledge there is no available information on hyperglycemia's effect on baseline or insulin responsive myocardial microvasculature. Given that acute "stress" hyperglycemia in the setting of acute coronary syndrome is such a strong predictor of mortality (1) defining a mechanism which might contribute to this microvascular dysfunction would be significant.

- **3. Provide a justification for the sample size used in this protocol.** See above
- 4. What is your plan for primary variable analysis? See above

5. What is your plan for secondary variable analysis?

The secondary variables include PWV, AI, PIFV, oxygen saturation of skeletal muscle (NIRS), blood pressure, heart rate, as well as plasma insulin, free fatty acid and blood glucose concentration. These variables will be compared within each admission and across all four admissions using repeated measures ANOVA.

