- Near infrared spectroscopy (NIRS) This is used to look at hemoglobin content (both oxygenated and deoxygenated) and oxygen saturation in the muscle. A small square fiber optic sensor (2 x 4 inches) will be placed on the skin over the forearm muscle. Light is emitted and as it travels through the different tissue in the arm (bone, fat, muscle, blood etc) it will create a mathematical measurement that has to do with density on the attached computer. The measurement takes 3-5 min.

A. Saline + Octreotide + Euglycemia (~10 hours)

On the day of admission, the subject will be admitted to the CRU at ~ 7:00AM. The subjects will have been asked to fast after 10PM the evening before. Female subjects will have a urine pregnancy test. We will insert 2 peripheral IV lines. One will be in an antecubital vein and this will be used for infusion of saline, octreotide, insulin, glucose and microbubbles. The second will be placed in the lower forearm of the same arm and will be used for sampling. This will be kept patent with a normal saline infusion.

After resting for 1 hour we will begin the study as follows.

- ➤ Blood pressure, heart rate and oxygen saturation will be obtained. If the oxygen saturation <90% the subject will be excluded.
- ➤ Blood will be drawn (~10 cc) for samples of glucose, insulin, and inflammatory cytokines from the sampling IV.
- ➤ We will begin a saline infusion at 30ml/hr.
- > This is considered time -90 min.

We will measure insulin every 30 minutes for duration of study (~18cc).

Between -30 and 0 minutes

- > We will measure NIRS of forearm muscle
- > Next we will measure PWV followed by AI
- Next we will measure FMD
- Next we will perform CEU of the heart and skeletal muscle
- > Subjects will be placed on a continuous cardiac monitor for 30 minutes following the end of the microbubble infusion. There will always be a resuscitation cart as well as qualified personnel available should the need arise.

Version Date: November 16, 2017

Page Number: 9 of 34

- ➤ We will repeat the blood sampling (~10cc) performed at time -90.
- We will begin an infusion of Octreotide (30ng/kg/min).
- ➤ We will begin an insulin infusion (dose is 0.15mU/kg body wt/min).
- We will also begin glucose infusion (20% variable rate) to maintain euglycemia.
- > This is considered time 0 min.
- ➤ We will measure plasma blood glucose every 10 min through 240 min (~23cc blood).

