- ➤ The values for blood glucose are measured immediately and used to adjust the rate of infusion of a glucose solution (20% dextrose) in order to maintain plasma glucose within 10% of the fasting concentration.
- We will repeat the entire sequence of vascular measurements between 210 and 240 minutes.
- ➤ We will also repeat blood draw for glucose, insulin and inflammatory cytokines (~10cc).
- ➤ At time 240 minutes the study is complete and the insulin and octreotide infusion will be stopped.
- Subject will be fed a meal.
- ➢ Blood glucose measurements will continue to be made at 10 minute intervals (~15 cc of blood) and the rate of the glucose infusion adjusted to maintain normal blood glucose levels. This will continue until blood glucose is within normal range without the need for the glucose infusion.
- ➤ We will also continue to test blood glucose every 15 minutes (~5cc blood) for one hour after glucose infusion stopped to be sure that blood glucose levels stay within normal range.

When the sampling for blood glucose is complete subjects will have all catheters removed and vital signs done. If stable they will be discharged.

Total blood taken for this admission is approximately ~91cc.

B. Octreotide + Hyperglycemia admission (~10hrs)

On the day of admission, the subject will be admitted to the CRU at ~ 7:00AM. The subjects will have been asked to fast after 10PM the evening before. Female subjects will have a urine pregnancy test. We will insert 2 peripheral IV lines. One will be in an antecubital vein and this will be used for infusion of octreotide, insulin, glucose and microbubbles. The second will be placed in the lower forearm of the same arm and will be used for sampling. This will be kept patent with a normal saline infusion.

After resting for 1 hour we will begin the study as follows.

- ➤ Blood pressure, heart rate and oxygen saturation will be obtained. If the oxygen saturation <90% the subject will be excluded.
- ➤ Blood will be drawn (~10cc) for samples of glucose, insulin, and inflammatory cytokines from the sampling IV.
- We will begin an infusion of Octreotide (30ng/kg/min).

Version Date: November 16, 2017

Page Number: 10 of 34

- We will also begin the insulin infusion (dose is 0.15mU/kg body wt/min).
- We will also begin glucose infusion (20% at variable rate) to maintain euglycemia.
- > This is considered time -90 min.
- ➤ We will draw blood every 10 min to measure blood glucose from time -90 min to 0 min (~12cc).

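### Admission A's before-after change mixes the octreotide package with about 4 hours of time and a repeat set of measurements, so a null result cannot by itself justify the before-after tests in B, C and D

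*Combined protocol and SAP*

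**What the plan says.** Statistical Considerations, item 2, plans a paired before-after comparison within each admission. For admission A it states that "this comparison will indicate whether 3 ½ hours of octreotide infusion with basal insulin replacement and maintenance of euglycemia per se influences microvascular perfusion". The result is then used as a condition: "if octreotide has no specific effect on the primary microvascular endpoint (MBV) then in protocols B, C, and D, we believe paired comparison" of baseline with end-of-study values is regarded as justified. The same item plans a 2-way ANOVA of A and B together to isolate hyperglycemia, and a comparison of changes between C and D. Among further comparisons it says that "comparing measures at D1 and A2 will allow assessment of the reproducibility of measures of microvascular function".

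Biomedical Research, item 1, gives the schedule. In A, the run-in is saline only ("We will begin a saline infusion at 30ml/hr", at −90 min). The first set of vascular measurements is taken "Between -30 and 0 minutes". Octreotide, basal insulin and glucose start after it ("This is considered time 0 min"), and then "We will repeat the entire sequence of vascular measurements between 210 and 240 minutes". In B, C and D, octreotide, basal insulin and glucose start at −90 min and octreotide continues to 240 min. The first measurements are at 0 min in B and at 90–120 min in C and D.

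**The concern.** A1 is the only octreotide-free set of measurements in the trial, and every 210–240 min set is taken on octreotide. Between A1 and A2 the subject also spends about 4 more hours fasting and at rest, after a 5-minute forearm cuff occlusion and a microbubble infusion. Any effect of that time or of repeating the measurements is counted in A2−A1 along with octreotide.

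The result also decides how B, C and D are read. Octreotide runs at both readings in those admissions, so a constant octreotide effect cancels from their before-after changes. Drift with time or repetition does not cancel, nor does any octreotide effect that develops after the first reading. A null A2−A1 could come from no drift and no octreotide effect, or from two effects of opposite sign. In the second case the condition is met and B's change is still biased. Downward drift in B would resemble the inhibition of perfusion by hyperglycemia that the protocol hypothesises.

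**Working it through.** **Timeline.** From the written steps for admissions A to D, in minutes on the study clock:

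| Reading | Clock | Time on octreotide | Set of the day |
|---|---|---|---|
| A1 | −30 to 0 | 0 | first |
| B1 | from 0 | from 90 | first |
| C1, D1 | 90–120 | 180–210 | first |
| A2 | 210–240 | 210–240 | second |
| B2, C2, D2 | 210–240 | 300–330 | second |

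The plan's 3½ h is reproduced: 210 − 0 = 210 min at the start of the A2 measurements, and 240 min (4 h) at their end. The A1-to-A2 interval is 210 − (−30) = 240 min, or 4 h. The pharmacy section (item 7a) gives infusions of 3.5 h for A and 5 h otherwise, whereas the steps give 4 h (0 to 240) and 5.5 h (−90 to 240). Those passages need reconciling. The table uses the steps; Figure 1 is not shown.

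**What each contrast contains.** Let O be the effect of the octreotide package (octreotide, basal insulin, glucose to hold euglycemia), H the effect of hyperglycemia, and T the effect of time plus repeat measurement between the first and last readings. Take O as constant once established, and T as the same in A and B.

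- A2−A1 = O + T. O cannot be estimated from A alone.
- B2−B1 = H + T. O cancels and T does not.
- B1−A1 = O at about 90 min, without T: both are first sets, at most about 30 min apart on the clock.
- A2−D1 = drift from 90–120 to 210–240 min plus the repeat effect. Study time differs by 210 − 90 = 120 min; octreotide exposure differs by 210 − 180 = 30 min.
- B2−A2 = H, at matched clock time and order, if O no longer changes between 3.5–4 h and 5–5.5 h.

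If O depends on duration, B1−A1 identifies only the 90-minute effect, and the 3½-hour effect stays confounded with T in all four admissions.

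**The A+B ANOVA does not separate them.**
- Treatment: [(B1+B2) − (A1+A2)]/2 = (O+H)/2.
- Time: [(A2−A1) + (B2−B1)]/2 = T + (O+H)/2.
- Interaction: (B2−B1) − (A2−A1) = H − O.

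No term is O or T alone.

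**Cancellation.** With T = −10% and O = +10%, A2−A1 = 0 and the condition is met, but B2−B1 = H − 10%.

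**Illustrative size.** No SD is stated. Suppose the plan's 80% power for a 30% difference (two-sided 0.05) came from a paired t-test. With 16 completers the standardised effect is 0.749, so the SD of differences is 30/0.749 ≈ 40%. With 22 it is 0.626, giving 30/0.626 ≈ 48%. The chance that A2−A1 is significant when O = 0 is then:

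| Assumed drift | n = 16, SD 40% | n = 22, SD 48% |
|---|---|---|
| 0 | 5% | 5% |
| 5% | 7.6% | 7.5% |
| 10% | 15.5% | 15.4% |
| 15% | 29.0% | 28.8% |
| 20% | 46.5% | 46.2% |

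Conversely, with 16 completers, a true 30% octreotide effect opposed by a 15% drift leaves a net 15%, detected in about 29% of trials instead of 80%.

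**The case against.** The strongest objection concerns the remedy. A reader might infer that A1 versus B1 should replace A2−A1 as the octreotide test. The documents do not support that. The question posed is about 3½ hours of the package, and A1 versus B1 answers for about 90 minutes. It compares different days, bringing in the variation that the plan hopes within-day pairing will reduce. It also contains no T, so as a condition for the tests in B, C and D it could be met while drift biased them. This objection stands: A1 versus B1 can only support A2−A1.

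Three other readings also go too far:

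- That the saline run-in is unused. A1 and B1 both enter the A+B ANOVA, and item 2 says other comparisons are possible. What is missing is a named contrast between them.
- That the trial repeats the gap it points out in an earlier clamp study ("The study did not test whether the octreotide (used in the pancreatic clamp) per se affected microvascular responses", Background). Admission A does test octreotide against an octreotide-free baseline; its fault is incomplete control. In the quoted sentence, *per se* also follows the whole package; octreotide alone is named only in the next sentence.
- That D1 versus A2 is invalid for reproducibility. The two are close in octreotide exposure, no reproducibility measure is specified, and a mean shift would not enter the SD of paired differences.

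It is also fair that octreotide is not a stated hypothesis, and that comparing changes between C and D has matched measurement times and octreotide schedules, so drift and octreotide cancel there. The exposed results are the single-admission before-after tests and the statement about octreotide.

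**Conclusion.** The concern holds in a limited form. A2−A1 estimates the octreotide package plus about 4 hours of time plus a repeat set of measurements. It should not be read as the package's effect *per se*, and a null value does not show that the before-after tests in B, C and D are free of drift. This follows from the written schedule and needs no numerical assumption.

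The size is unknown. The 5–15% drift range is assumed, and the resulting 8–29% chance of a spurious octreotide finding also rests on an SD inferred from the power statement by assuming a paired t-test. These figures show what is possible; nothing in the documents shows that drift occurs.

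A reader might go on to infer that the trial's hyperglycemia conclusions fail. They need not: the C-versus-D comparison is protected, and B2 versus A2 is matched on clock time and measurement order, subject to the octreotide effect having levelled off. This is a low-cost improvement that changes what can be concluded from A and from the single-admission tests.

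**What to change.** 1. Report A2−A1 as the octreotide package plus time and repeat measurement, and do not let a null value alone justify the before-after tests in B, C and D.
2. Add the within-subject A1 versus B1 contrast beside A2−A1, as a supporting estimate of the package at about 90 min. State that extending it to 3½ h assumes a constant effect.
3. Report the mean A2−D1 difference, with its confidence interval, as an estimate of time and repeat-measurement drift at similar octreotide exposure, as well as any reproducibility measure. It matches the clock times and order of C1 to C2 and D1 to D2.
4. Treat single-admission before-after results in B, C and D as supportive. Base conclusions on between-admission comparisons at matched times, such as B2 versus A2 and C versus D.

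The cost is wording and two paired contrasts on data already planned, with no new visits or procedures. The limits should be stated: A1 versus B1 covers only about 90 min of octreotide and adds day-to-day noise, and A2−D1 covers only 2 h of drift, less than the roughly 3½ h between B1 and B2.

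### The A vs B and C vs D contrasts on microvascular perfusion are specified only as a two-way ANOVA with no subject term, although every subject completes all four admissions

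*Combined protocol and SAP*

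**What the plan says.** Under Study Design item 1 each subject is his or her own control, and under item 2 each completes all four arms in random order.

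Statistical Considerations item 2 opens with pairing: "By design, each of the above protocols affords a paired comparison of the changes which occur between measurements obtained at baseline". The other half of each pair is measured when that admission's infusions finish, so this is change inside one admission. The next sentence reads "Principal endpoints are the changes in microvascular perfusion in both skeletal and cardiac" muscle.

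The comparisons between admissions come later in item 2:

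- **A vs B:** "Combined protocols A and B analyzed using a 2-way ANOVA will allow analysis of whether time or treatment differences exist", and this "will delineate the effect of hyperglycemia per se on skeletal and cardiac muscle microvascular perfusion". The factors named are time and treatment.
- **C vs D:** comparison of the "changes of indices of microvascular perfusion between protocol C and D (2-way ANOVA") is to show whether hyperglycemia induces resistance to insulin's microvascular action. No factors are named.

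Item 4 adds nothing: "What is your plan for primary variable analysis? See above". Item 5 does name a within-subject method, but for its own list of secondary variables: "These variables will be compared within each admission and across all four admissions using repeated measures ANOVA". That list contains neither microvascular blood volume nor flow-mediated dilation, the two endpoints that the Brief Summary calls primary.

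**The concern.** A vs B carries hypothesis (a), the effect of hyperglycemia itself. C vs D carries the insulin-resistance question. In both, the two sets of measurements come from the same people, so they are correlated. An ANOVA on time and treatment alone treats them as independent and puts the wrong variance in the error term.

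The direction of the error depends on which line of the ANOVA table is read. For the condition-by-time interaction, or an unpaired test of changes, the error term is too large. The risk is then a missed effect and wider intervals. For the treatment main effect on raw levels, the error term can be too small, and the risk is a false positive. The A vs B sentence speaks of time or treatment differences and never mentions the interaction, so an analyst could reasonably read off the main effect.

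**Working it through.** **The plan's own figure.** Human Participants item 2 gives 22 subjects for at least 80% power, two-sided 0.05. Item 2 of the statistical section gives 20 per group, at least 16 completing, and a 30% difference. No SD or correlation is given, so neither can be reproduced. Back-solving with paired noncentral-t power, 80% needs a standardised paired effect d = 0.626 at n=22 (SD of the difference 30/0.626 = 47.9%) or 0.749 at n=16 (30/0.749 = 40.0%).

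**1. Test of the difference in change.** Let each change have variance s², with correlation ρ between a subject's changes on the two admissions.

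- True variance of the mean difference: 2s²(1−ρ)/n
- Variance used without subject: 2s²/n, on 2n−2 = 42 df
- Paired test: correct variance, on n−1 = 21 df

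Fixing d so that the paired test has 80% power at n=22, power without subject is approximately Φ(d√n − t₄₂/√(1−ρ)), with d√n = 0.626 × 4.690 = 2.936 and t₄₂ = 2.018:

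- ρ = 0: Φ(2.936 − 2.018) = Φ(0.918) = 82%
- ρ = 0.1: Φ(2.936 − 2.127) = Φ(0.809) = 79%
- ρ = 0.3: Φ(2.936 − 2.412) = Φ(0.524) = 70%
- ρ = 0.5: Φ(2.936 − 2.854) = Φ(0.082) = 53%

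Simulation agrees to within a point at n=22:

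| ρ (assumed) | 0 | 0.1 | 0.2 | 0.3 | 0.5 |
|---|---|---|---|---|---|
| Power without subject, n=22 (paired 80%) | 82% | 79% | 75% | 70% | 54% |
| Power without subject, n=16, same d (paired 65%) | 68% | 64% | 59% | 53% | 37% |
| 95% CI width relative to paired, n=22 | 0.98 | 1.03 | 1.09 | 1.17 | 1.38 |
| Type I error without subject, n=22 | 5.0% | about 4% | about 3% | 2.1% | 0.8% |

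The break-even correlation at n=22 is about 0.07-0.09. Below it the unpaired test is marginally better.

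**2. A more favourable calibration.** Item 2 also says "we have found that 12-14 subjects are sufficient to detect a 30% difference in microvascular function in response to insulin". If that means 80% paired power at 12 to 14 subjects (an inference; neither the power nor the test is stated there), then d = 0.889 to 0.810. Paired power is 95-98% at n=22 and 86-91% at n=16. Without subject it is 91-96% and 82-90% at n=22 for ρ = 0.3 and 0.5, and 78-86% and 64-74% at n=16.

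**3. Treatment main effect on raw levels.** Take four values per subject (two admissions by two times), unit variance, within-day correlation w and between-day correlation b. The contrast is the mean of the two B values minus the mean of the two A values.

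- True variance: (1 + w − 2b)/n
- Variance used without subject: 1/n

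The test is too liberal whenever w > 2b.

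- w = 0.7, b = 0.2: ratio 1 + 0.7 − 0.4 = 1.3; simulated type I error about 9%
- w = 0.7, b = 0.1: ratio 1 + 0.7 − 0.2 = 1.5; simulated type I error about 11%
- w = 0.6, b = 0.3: ratio 1.0; about 5%
- w = 0.8, b = 0.5: ratio 0.8; about 3%

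The interaction in the same model has true variance 4(1 − w)/n against an assumed 4/n, so with non-negative w it is never liberal.

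**The case against.** The strongest reply is that this is shorthand. The own-control design is stated, item 2 opens with pairing, and the team names repeated-measures ANOVA in item 5, so it knows the method. For C vs D the quantity compared is already a change, so time is absorbed and a second factor is needed; subject is the natural one, and condition plus subject on changes is exactly the paired test. Hypothesis (a) also has other support: if octreotide has no effect in A, item 2 allows a paired baseline-to-end comparison within B.

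Much of this stands. It makes within-subject intent plausible and limits what hangs on the wording. It does not close the gap. The stated pairing does not reach the difference between two admissions. The within-B comparison is conditional. The endpoints that matter most have a vaguer model than the secondary ones.

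The sizes are also open to challenge. The power losses need people to differ consistently in how much they respond. If subjects differ only in level, changes on two admissions are uncorrelated and a paired test of changes gains nothing.

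A reader might infer three stronger things that the documents do not support:

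- That the plan chooses an unpaired analysis. Subject is unmentioned, not excluded.
- That omitting subject is at least safe, so any positive result would stand. This holds for the interaction and for the test of changes with non-negative correlation, but not for the treatment main effect.
- That false positives are inflated generally. That needs the main effect on raw levels and w > 2b.

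**Conclusion.** The gap is real and should be closed, as under-specification with a concrete better method rather than as a demonstrated error. For the test that answers the question, omitting subject costs little or nothing at a correlation of changes near zero. It costs about 10 points of power at 0.3 and 26 at 0.5 (80% to 70% and 54%) if the study has 80% paired power at n=22, and less under the more favourable calibration. For the treatment main effect, type I error could reach about 9-11% under the correlations shown. Every correlation and effect size here is assumed. That the plan leaves the model open rests on the text alone.

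**What to change.** In Statistical Considerations item 2, replace the two-way ANOVA wording for both contrasts with a sentence such as: *A vs B and C vs D will each be tested by a paired (within-subject) comparison of the baseline-to-end change between the two admissions.* Equivalently, name the condition-by-time interaction in a two-way repeated-measures ANOVA, tested against the subject-by-condition-by-time error. State that this, not the treatment main effect, is the test.

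Two near-equivalents do not do the job:

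- **Subject as a block with one pooled residual.** At n=22 this has 88 − 21 − 4 = 63 error df and is not the paired test.
- **A mixed model with random subject and subject-by-admission only.** It forces a subject's changes on two admissions to be uncorrelated, so with complete data it generally reproduces the unpaired test. If a mixed model is used to keep incomplete subjects, it needs a subject-by-time random term as well, or an unstructured within-subject covariance.

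The cost is a sentence of text and a fall in error df from 42 to 21 at n=22. If changes are uncorrelated across admissions, that loses about 2 points of power at n=22 (82% to 80%) and 3 at n=16 (68% to 65%).
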